6.2 Dose escalation guidelines

Not applicable to this study.

6.3 Dose modifications

6.3.1 Dose modification and dose delay

For patients who do not tolerate the protocol-specified dosing schedule, dose adjustments are permitted in order to allow the patients to continue the study treatment. Any changes in ceritinib administration must be recorded on the Dosage Administration Record eCRF.

General guidelines for dose modifications for toxicities other than those listed in Table 6-3:

For grade 1 and tolerable grade 2 treatment-related toxicities, patients may continue at the current dose of study treatment. For intolerable grade 2 treatment-related toxicities, dosing should be interrupted until resolution to grade 1 or lower followed by dose reduction to the next dose level.

For grade 3 or grade 4 treatment-related toxicity that is not considered by the investigator to be life-threatening, patients should interrupt study treatment until resolution to grade 1 or lower; then study treatment may continue following a dose reduction to the next dose level, if, in the opinion of the Investigator, the patient continues to experience clinical benefit. For any

grade 3 or 4 treatment-related toxicity that is considered by the investigator to be life-threatening, permanently discontinue study treatment.

More detailed ceritinib dose modification guidelines for selected toxicities are described in [Section 6.3.3](#) and [Table 6-3](#). Any planned variance from these guidelines in view of patient safety must first be discussed with the sponsor unless there is an urgent need for action.

All dose modifications, interruptions or discontinuations must be based on the worst preceding toxicity as graded by the NCI Clinical Toxicity Criteria (NCI-CTCAE version 4.03).

6.3.2 Treatment interruption and treatment discontinuation

If the administration of ceritinib is temporarily interrupted for reasons other than toxicity, then treatment with ceritinib may be resumed at the same dose. The same applies if the patient experiences an unacceptable toxicity not specifically described in [Table 6-3](#), provided this toxicity resolved to \leq CTCAE grade 1.

If the treatment with ceritinib is withheld due to toxicity, scheduled visits and all assessments should continue to be performed (with the exception of the dosing of the withheld study drug), as described in [Table 7-1](#).

If the treatment with ceritinib dosing is withheld for more than 28 consecutive days (counting from the first day when a dose was missed), due to treatment-related toxicity, then ceritinib should be permanently discontinued except in cases where the investigator believes the patient continues to derive clinical benefit. In such cases, treatment with ceritinib may be resumed at a lower dose. See [Section 6.1.3](#) for exception in case of isolated brain progression with controlled disease outside of the brain.

Patients whose treatment is temporarily interrupted or permanently discontinued due to a study drug related AE or an abnormal laboratory value must be followed until resolution or stabilization of the event, whichever comes first, including all study assessments appropriate to monitor the event. Detailed guidelines for follow-up of study drug related AEs or abnormal laboratory values must be followed as described in [Section 6.3.4](#).

All patients will be followed for safety until 30 days after the last dose of ceritinib. Patients whose treatment is temporarily interrupted or permanently discontinued due to an AE or abnormal laboratory value must be followed until resolution or stabilization of the event, whichever comes first, including all study assessments appropriate to monitor the event.

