1.2.1.2 Clinical experience

1.2.1.2.1 Clinical safety and tolerability

Ceritinib is associated with a manageable safety profile. For the 255 patients treated at the recommended dose of 750 mg in the ongoing study [REDACTED]

The

most common adverse events regardless of study drug relationship (incidence $\geq 25\%$) were diarrhea, nausea, vomiting, alanine aminotransferase (ALT) increased, fatigue, abdominal pain, decreased appetite, aspartate aminotransferase (AST) increased, and constipation.

The incidence of grade 3-4 AEs, regardless of study drug relationship was $<10\%$ for all AEs except ALT increased (26.7%) (Table 1-1). The incidence of grade 3-4 AEs, regardless of study drug relationship, was $<5\%$ for all AEs except AST increased (8.2%), diarrhea (5.9%), hyperglycemia (5.5%), lipase increased (5.1%), and blood alkaline phosphatase (ALP) increased (5.1%).

Table 1-1 All grades (at least 5%) and grade 3-4 adverse events, regardless of study drug relationship, by preferred term in patients treated in the 750 mg dose group

Preferred term	Ceritinib 750 mg N=255	
	All Grades n (%)	Grade 3/4 n (%)
Total	255 (100.0)	184 (72.2)
Diarrhea	219 (85.9)	15 (5.9)
Nausea	205 (80.4)	11 (4.3)
Vomiting	153 (60.0)	10 (3.9)
Alanine Aminotransferase Increased	110 (43.1)	68 (26.7)
Fatigue	102 (40.0)	10 (3.9)
Abdominal Pain	91 (35.7)	3 (1.2)
Decreased Appetite	87 (34.1)	2 (0.8)
Aspartate Aminotransferase Increased	78 (30.6)	21 (8.2)
Constipation	73 (28.6)	0
Cough	62 (24.3)	0
Abdominal Pain Upper	58 (22.7)	2 (0.8)
Dyspnea	47 (18.4)	8 (3.1)
Asthenia	45 (17.6)	2 (0.8)
Blood Alkaline Phosphatase Increased	45 (17.6)	13 (5.1)
Back Pain	43 (16.9)	1 (0.4)
Headache	41 (16.1)	3 (1.2)
Weight Decreased	39 (15.3)	4 (1.6)
Blood Creatinine Increased	39 (15.3)	0
Pyrexia	38 (14.9)	0
Rash	32 (12.5)	0
Insomnia	31 (12.2)	0
Dyspepsia	26 (10.2)	1 (0.4)
Hypokalemia	26 (10.2)	11 (4.3)
Dizziness	26 (10.2)	0
Musculoskeletal Pain	25 (9.8)	0
Anemia	24 (9.4)	9 (3.5)
Edema Peripheral	24 (9.4)	0
Non-Cardiac Chest Pain	24 (9.4)	2 (0.8)
Hypomagnesemia	22 (8.6)	0

Preferred term	Ceritinib 750 mg N=255	
	All Grades n (%)	Grade 3/4 n (%)
Productive Cough	22 (8.6)	0
Arthralgia	21 (8.2)	0
Hyperglycemia	21 (8.2)	14 (5.5)
Musculoskeletal Chest Pain	21 (8.2)	0
Lipase Increased	20 (7.8)	13 (5.1)
Pneumonia	20 (7.8)	10 (3.9)
Pain In Extremity	17 (6.7)	0
Muscle Spasms	17 (6.7)	0
Pruritus	17 (6.7)	1 (0.4)
Hyponatremia	16 (6.3)	9 (3.5)
Chest Discomfort	16 (6.3)	0
Dehydration	16 (6.3)	2 (0.8)

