6.3.3 Criteria for ceritinib dose modifications

A ceritinib dose reduction will follow the guidelines described in [Table 6-2](#). For each patient, a maximum of 3 dose modifications (in 150 mg decrements per reduction) is allowed after which the patient must be discontinued from treatment with ceritinib. Once the dose of ceritinib has been reduced, it cannot be re-escalated. If a patient continues treatment with ceritinib after RECIST-defined PD as determined by the investigator, the criteria for dose modification will also apply.

[figure not shown]

Table 6-2 Dose reduction steps for ceritinib

[figure not shown]
Ceritinib dose levels	Dose* and schedule
Starting dose level	750 qd continuously
Dose level – 1	600 qd continuously
Dose level – 2	450 qd continuously
Dose level – 3	300 qd continuously **

*Dose reduction should be based on the worst preceding toxicity per NCI-CTCAE version 4.03
**Dose reduction below 300 mg/day is not allowed. If a dose reduction below 300 mg/day is required, the patient should be permanently discontinued from Ceritinib

[figure not shown]
Guidelines for dose modification and dose interruption of ceritinib are described in [Table 6-3](#).

Table 6-3 Criteria for dose reduction, interruption and re-initiation of ceritinib treatment

[figure not shown]
Worst toxicity (CTCAE 4.03 Grade)*	Dose Modifications for ceritinib
HEMATOLOGICAL	
Neutropenia (ANC)	
Grade 1 (ANC < LLN - $1.5 \times 10^9/L$) Grade 2 (ANC < 1.5 and $\geq 1.0 \times 10^9/L$) Grade 3 (ANC < 1.0 and $\geq 0.5 \times 10^9/L$)	Recommendation: Maintain dose level
Grade 4 (ANC < $0.5 \times 10^9/L$)	Mandatory: Omit dose until resolved to \leq Grade 2, then it is recommended: If resolved in ≤ 7 days, to maintain dose level If resolved in > 7 days, to \downarrow 1 dose level
Febrile neutropenia (ANC < $1.0 \times 10^9/L$, with a single temperature of ≥ 38.3 °C or a sustained temperature of ≥ 38 °C for more than one hour)	Mandatory: Omit dose until clinically resolved and neutropenia \leq Grade 2, then \downarrow 1 dose level
Thrombocytopenia	
Grade 1 (PLT < LLN - $75 \times 10^9/L$) Grade 2 (PLT < 75 and $\geq 50 \times 10^9/L$)	Recommendation: Maintain dose level
Grade 3 (PLT < 50 and $\geq 25 \times 10^9/L$)	Mandatory: Omit dose until resolved to \leq Grade 2, then it is recommended: If resolved in ≤ 7 days, to maintain dose level If resolved in > 7 days, to \downarrow 1 dose level

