Persistent hyperglycemia (glucose > 250 mg/dL, despite minimization of dose of steroids and optimal anti-hyperglycemic therapy)	Recommendation: Omit dose until hyperglycemia is adequately controlled, then resume ceritinib at ↓ 1 dose level If adequate hyperglycemic control cannot be achieved with optimal medical management, permanently discontinue patient from ceritinib.
GENERAL DISORDERS	
Fatigue (asthenia)	
Grade 1 or 2	Recommendation: Maintain dose level
Grade 3	Recommendation: If grade 3 fatigue resolves to Grade 2 in ≤ 7 days, maintain dose level If grade 3 fatigue lasts > 7 days, omit dose until resolved to ≤ Grade 2 and then ↓ dose level

Worst toxicity (CTCAE 4.03 Grade)*	Dose Modifications for ceritinib
PULMONARY	

Notes:
 
 • Recommendation: Withhold ceritinib for acute onset of new or progressive unexplained pulmonary symptoms, such as dyspnea, cough and fever and during diagnostic workup for pneumonitis/ILD. • During evaluation of potential grade 2, 3, and 4 pneumonitis, if an infectious etiology is confirmed (i.e., pneumonia) and pneumonitis is excluded, ceritinib dosing may resume at current dose level after the pneumonia resolves. 	
PNEUMONITIS	
Any Grade treatment-related ILD/pneumonitis	Mandatory: Permanently discontinue patient from ceritinib
CARDIAC	
Electrocardiogram QT corrected (QTc) interval prolonged*****	
Grade 1 (QTc 450-480 ms) Grade 2 (QTc 481-500 ms)	Recommendation: Maintain dose level
Grade 3 (QTc ≥ 501 ms on at least two separate ECGs)	
Mandatory: Omit dose until QTc is < 481ms, then ↓ 1 dose level
 
- Assess the quality of the ECG recording and the QT value and repeat if needed
 
Repeat ECG in 24 hours, or less, as clinically indicated; continue monitoring as clinically indicated until QTc < 481 ms
 
In addition:
 
 -Determine the serum electrolyte levels (in particular hypokalemia, hypomagnesemia). If abnormal, correct abnormalities before resuming study drug treatment - Review concomitant medication use for drugs with the potential to increase the risk of drug exposure related to QT prolongation - Consider collecting [REDACTED] sample and record time and date of last study drug intake 
After resumption of dosing:
 
 -Repeat ECGs 7 days after dose resumption for all patients who had therapy interrupted due to QTc ≥ 501 ms.

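### For treatment-related toxicities outside Table 6-3, Protocol 6.3.1 directs restart one dose level lower, while 6.3.2 as worded permits restart at the same dose

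*Protocol*

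**What the plan says.** Protocol 6.3.1 sets general guidelines for toxicities that Table 6-3 does not list, and each of its dose rules concerns treatment-related events. Grade 1 and tolerable grade 2 need no change of dose. For intolerable grade 2, "dosing should be interrupted until resolution to grade 1 or lower followed by dose reduction to the next dose level". For grade 3 or 4 that the investigator does not consider life-threatening, treatment is interrupted until grade 1 or lower; "then study treatment may continue following a dose reduction to the next dose level", if the patient still benefits. Life-threatening grade 3 or 4 means permanent discontinuation. The section also requires any planned variance to be discussed with the sponsor first, unless action is urgent.

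Protocol 6.3.2 opens with interruptions for reasons other than toxicity, after which the same dose may be resumed. It continues: "The same applies if the patient experiences an unacceptable toxicity not specifically described in" Table 6-3, on condition that the event has resolved to grade 1 or lower. A later rule in 6.3.2 covers treatment withheld for more than 28 consecutive days "due to treatment-related toxicity, then ceritinib should be permanently discontinued except in cases where the investigator believes the patient continues to derive clinical benefit". It adds: "In such cases, treatment with ceritinib may be resumed at a lower dose".

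Table 6-2 in 6.3.3 gives the levels 750, 600, 450 and 300 mg, with a floor: "If a dose reduction below 300 mg/day is required, the patient should be permanently discontinued from Ceritinib". Section 6.3.3 also rules out re-escalation after a reduction.

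**The concern.** Both sections address a toxicity that is absent from Table 6-3, has led to an interruption, and has resolved to grade 1 or lower. For a treatment-related event of this kind, 6.3.1 directs the next lower dose and 6.3.2 permits the previous one. An investigator who relies on 6.3.2 would give a dose above the one 6.3.1 directs, and could not tell from the protocol whether that was a deviation.

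What is at stake is the dose a patient takes after a drug-related toxicity. Because reductions are not reversed, the difference can last for the rest of treatment. At 300 mg it decides whether the patient stays on ceritinib at all.

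**Working it through.** The protocol gives no figure for this point, so the check is a comparison of texts followed by arithmetic on Table 6-2.

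**1. Where the sections meet.** Treatment-related events not in Table 6-3:

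| Situation | 6.3.1 | 6.3.2 as worded | Result |
|---|---|---|---|
| Grade 1 or tolerable grade 2 | Continue at current dose | No restart to decide | No conflict |
| Intolerable grade 2, resolved, held 28 days or less | One level lower | Same dose permitted | Conflict |
| Grade 3/4, not life-threatening, resolved, held 28 days or less | One level lower, if benefit continues | Same dose permitted | Conflict |
| Either of these, held more than 28 days | One level lower | Stop, or a lower dose if benefit continues | Compatible |
| Life-threatening grade 3/4 | Permanent discontinuation | No restart to decide | Not part of this point |

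The conflict is therefore confined to interruptions of 28 days or less.

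**2. Is a reconciling rule written down?** Two would work: 6.3.2 covers only unrelated toxicity, or 6.3.1 prevails as the more specific text. Neither is stated. The 28-day rule in 6.3.2 names the treatment-related class expressly, and the same-dose sentence in the same section does not.

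**3. Size per event.** Let a be the dose before interruption (the 6.3.2 restart) and b the next level in Table 6-2 (the 6.3.1 restart). Difference = a − b; relative excess = 100 × (a − b)/b.

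- 750 vs 600 mg: 150 mg; 100 × 150/600 = 25%
- 600 vs 450 mg: 150 mg; 100 × 150/450 = 33.3%
- 450 vs 300 mg: 150 mg; 100 × 150/300 = 50%
- At 300 mg: there is no lower level, so 6.3.1 leads to permanent discontinuation, while 6.3.2 would let 300 mg continue.

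**4. Comparison with Table 6-3.** For listed events, the table itself accepts a same-dose restart after resolved grade 2 diarrhea or vomiting at first occurrence, and after grade 2 creatinine that resolves within 7 days. For grade 3 AST/ALT, creatinine, diarrhea, nausea and vomiting, it makes a one-level reduction mandatory. It keeps the dose for some short-lived higher-grade events (for example grade 3 thrombocytopenia resolving within 7 days), but ties this to a named toxicity and a time limit. The 6.3.2 sentence has neither. The case is therefore stronger for grade 3/4 than for grade 2.

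**The case against.** The strongest reply is that these are not two opposing orders. Section 6.3.1 is headed as guidelines and mostly says should; 6.3.2 says may. A site that always reduces satisfies both, and 6.3.1 provides a sponsor-discussion route for planned variance. The 6.3.2 sentence extends a rule about non-toxicity interruptions, while each 6.3.1 dose rule is graded and limited to treatment-related events. Together with the lower-dose restart in the 28-day rule, this makes the harmonious reading plausible, perhaps intended. All of that stands, and it limits the point to a directed reduction against a permitted same-dose restart. It does not remove the overlap: a site using 6.3.2 as written has no reason to think that it is planning a variance.

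Timing also counts against urgency. Enrollment ended on 31 August 2017, and the Amendment 6 rationale reports 45 patients still on ceritinib, who were to move to a rollover study or other access. Few patients may be dosed under this sentence.

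Four stronger inferences are tempting but unsupported:

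- **A frequency.** A reader might add up grade 3/4 counts of unlisted terms in Table 1-1 and quote a maximum share of patients. That table reports "All grades (at least 5%) and grade 3-4 adverse events, regardless of study drug relationship, by preferred term", whereas the conflict needs a related event. The total also depends on whether one counts hypokalemia (11), named in Table 6-3 only as something to check under QTc prolongation, or dyspnea (8), abdominal pain (3) and upper abdominal pain (2), symptoms covered there by notes on withholding drug and working up, without a restart dose for the symptom. Terms below 5% and intolerable grade 2 events are not shown. No percentage ceiling is defensible.
- **Life-threatening events.** The 6.3.2 sentence does not exclude them by name, but it concerns resuming treatment, and 6.3.1 orders permanent discontinuation.
- **Distorted dose summaries.** SAP 4.5 works from doses actually taken, and SAP 2.6 uses a fixed planned 750 mg/day for relative dose intensity. The tables remain correct descriptions of the dosing given.
- **An effect on the primary result.** Nothing in the ORR definition, its exact interval or the sample size depends on this rule.

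**Conclusion.** The inconsistency is real as worded. For treatment-related toxicity outside Table 6-3, interrupted for 28 days or less and resolved to grade 1 or lower, 6.3.1 directs a restart one level down and 6.3.2 permits the previous dose, with no stated order of precedence. Each such event carries a 150 mg difference, or continuing versus stopping at 300 mg. The frequency is unknown and could be zero, because it needs a related unlisted event, an interruption, resolution and a site that chooses the same dose.

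This rests on reading the 6.3.2 sentence without a limit that it does not contain. If the sponsor meant unrelated events only, the defect is one of drafting. It is a minor inconsistency in a dosing instruction that should be corrected, and it leaves the planned efficacy estimates untouched.

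**What to change.** Replace the second sentence of 6.3.2 with:

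> The same applies if ceritinib is interrupted for a toxicity that is not related to ceritinib and is not described in Table 6-3, provided this toxicity resolved to ≤ CTCAE grade 1. For treatment-related toxicities not described in Table 6-3, follow Section 6.3.1.

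The sponsor should first confirm that this is the intended reading, since the protocol does not state it.

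The cost is one sentence, made by written amendment with the approvals that section 12.1 requires: the sponsor, health authorities where required, and the ethics bodies. It bears only on patients still taking ceritinib. No assessment, sample-size figure or efficacy analysis changes.

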6.3.3 Criteria for ceritinib dose modifications

A ceritinib dose reduction will follow the guidelines described in [Table 6-2](#). For each patient, a maximum of 3 dose modifications (in 150 mg decrements per reduction) is allowed after which the patient must be discontinued from treatment with ceritinib. Once the dose of ceritinib has been reduced, it cannot be re-escalated. If a patient continues treatment with ceritinib after RECIST-defined PD as determined by the investigator, the criteria for dose modification will also apply.

[figure not shown]

Table 6-2 Dose reduction steps for ceritinib

[figure not shown]
Ceritinib dose levels	Dose* and schedule
Starting dose level	750 qd continuously
Dose level – 1	600 qd continuously
Dose level – 2	450 qd continuously
Dose level – 3	300 qd continuously **

*Dose reduction should be based on the worst preceding toxicity per NCI-CTCAE version 4.03
**Dose reduction below 300 mg/day is not allowed. If a dose reduction below 300 mg/day is required, the patient should be permanently discontinued from Ceritinib

[figure not shown]
Guidelines for dose modification and dose interruption of ceritinib are described in [Table 6-3](#).

Table 6-3 Criteria for dose reduction, interruption and re-initiation of ceritinib treatment

[figure not shown]
Worst toxicity (CTCAE 4.03 Grade)*	Dose Modifications for ceritinib
HEMATOLOGICAL	
Neutropenia (ANC)	
Grade 1 (ANC < LLN - $1.5 \times 10^9/L$) Grade 2 (ANC < 1.5 and $\geq 1.0 \times 10^9/L$) Grade 3 (ANC < 1.0 and $\geq 0.5 \times 10^9/L$)	Recommendation: Maintain dose level
Grade 4 (ANC < $0.5 \times 10^9/L$)	Mandatory: Omit dose until resolved to \leq Grade 2, then it is recommended: If resolved in ≤ 7 days, to maintain dose level If resolved in > 7 days, to \downarrow 1 dose level
Febrile neutropenia (ANC < $1.0 \times 10^9/L$, with a single temperature of ≥ 38.3 °C or a sustained temperature of ≥ 38 °C for more than one hour)	Mandatory: Omit dose until clinically resolved and neutropenia \leq Grade 2, then \downarrow 1 dose level
Thrombocytopenia	
Grade 1 (PLT < LLN - $75 \times 10^9/L$) Grade 2 (PLT < 75 and $\geq 50 \times 10^9/L$)	Recommendation: Maintain dose level
Grade 3 (PLT < 50 and $\geq 25 \times 10^9/L$)	Mandatory: Omit dose until resolved to \leq Grade 2, then it is recommended: If resolved in ≤ 7 days, to maintain dose level If resolved in > 7 days, to \downarrow 1 dose level
Grade 4 (PLT < $25 \times 10^9/L$)	Mandatory: Omit dose until resolved to \leq Grade 2, then \downarrow 1 dose level
HEPATIC	
Alkaline phosphatase and/or Gamma-glutamyl transpeptidase (GGT)	
Isolated elevations of any grade	Recommendation: Maintain dose level
Total Bilirubin** (for patients with Gilbert Syndrome these dose modifications apply to changes in direct [conjugated] bilirubin only)	
Grade 1 ($> ULN$ and $\leq 1.5 \times ULN$)	Recommendation: Maintain dose level with liver function test (LFTs)*** monitored as per protocol
Grade 2 (> 1.5 and $\leq 3.0 \times ULN$) with ALT or AST $\leq 3.0 \times ULN$	Mandatory: Omit dose until resolved to \leq Grade 1, then it is recommended: If resolved in ≤ 7 days, to maintain dose level If resolved in > 7 days, to \downarrow 1 dose level

[figure not shown]
Worst toxicity (CTCAE 4.03 Grade)*	Dose Modifications for ceritinib
Grade 3 (> 3.0 and ≤ 10.0 x ULN) with ALT or AST ≤ 3.0 x ULN	Mandatory: Omit dose until resolved to ≤ Grade 1, then it is recommended: If resolved in ≤ 7 days, to ↓ 1 dose level If resolved in > 7 days, to discontinue patient from ceritinib
Grade 4 (> 10.0 x ULN)	Mandatory: Permanently discontinue patient from ceritinib
AST or ALT	
Grade 1 (> ULN and ≤ 3.0 x ULN)	Recommendation: Maintain dose level with LFTs*** monitored per protocol
Grade 2 (> 3.0 and ≤ 5.0 x ULN) without total bilirubin elevation to > 2.0 x ULN	Recommendation: Maintain dose level with LFTs*** monitored per protocol
Grade 3 (> 5.0 and ≤ 20.0 x ULN) without total bilirubin elevation to > 2.0 x ULN	Mandatory: Omit dose until resolved to ≤ Grade 1, then ↓ 1 dose level
Grade 4 (> 20.0 x ULN) without total bilirubin elevation to > 2.0 x ULN	Mandatory: Omit dose until resolved to ≤ Grade 1, then ↓ 1 dose level
AST or ALT and concurrent Total bilirubin	
AST or ALT > 3.0 x ULN with total bilirubin > 2.0 x ULN in the absence of cholestasis or hemolysis	Mandatory: Permanently discontinue patient from ceritinib Refer to Section 6.3.4.2 for additional follow-up
RENAL	
Serum creatinine	
Grade 1 (>1 and ≤1.5 x baseline; >ULN and ≤ 1.5 x ULN)	Recommendation: Maintain dose level
Grade 2 (> 1.5 and ≤ 3 x baseline; >1.5 and ≤3.0 x ULN)	Recommendation: Omit dose until resolved to ≤ Grade 1, then it is recommended: If resolved in ≤ 7 days, then maintain dose level If resolved in > 7 days, then ↓ 1 dose level
Grade 3 (>3.0 x baseline; > 3.0 and ≤ 6.0 x ULN)	Mandatory: Omit dose until resolved to ≤ Grade 1, then ↓ 1 dose level
Grade 4 (> 6.0 x ULN)	Mandatory: Permanently discontinue patient from ceritinib
PANCREATIC	
Amylase and/or lipase elevations (in the absence of clinical symptoms)	
Grade 1 (> ULN and ≤1.5 x ULN)	Recommendation: Maintain dose level
Grade 2 (>1.5 - 2.0 x ULN)	Recommendation: Maintain dose level
Grade ≥3 (> 2.0 x ULN)	Mandatory: Omit dose until resolved to ≤ Grade 1, then ↓ 1 dose level
Note: Withhold ceritinib for acute onset of new or progressive unexplained abdominal symptoms, such as severe pain or vomiting; perform diagnostic procedures (e.g., abdominal CT scan or ultrasound) to exclude pancreatic pathology.	

[figure not shown]
Worst toxicity (CTCAE 4.03 Grade)*	Dose Modifications for ceritinib
GASTROINTESTINAL	
Diarrhea****	
Grade 1	Recommendation: Maintain dose level but adjust anti-diarrhea treatment
Grade 2 (despite maximal anti-diarrheal medication)	Recommendation: Omit dose until resolved to ≤ Grade 1, then maintain dose level. If diarrhea returns as ≥ Grade 2, then omit dose until resolved to ≤ Grade 1, then ↓ 1 dose level
Grade 3 (despite maximal anti-diarrheal medication)	Mandatory: Omit dose until resolved to ≤ Grade 1, then ↓ 1 dose level
Grade 4 (despite maximal anti-diarrheal medication)	Mandatory: Omit dose until resolved to ≤ Grade 1, then ↓ 1 dose level
Nausea*****	
Grade 1 or 2	Recommendation: Maintain dose level but adjust anti-emetic treatment
Grade 3 (despite standard anti-emetics)	Mandatory: Omit dose until resolved to ≤ Grade 1, then ↓ 1 dose level
Vomiting*****	
Grade 1	Recommendation: Maintain dose level but adjust anti-emetic treatment
Grade 2 (despite standard anti-emetics)	Recommendation: Omit dose until resolved to ≤ Grade 1, then maintain dose level. If vomiting returns as ≥ Grade 2, then suspend dose until resolved to ≤ Grade 1, then ↓ 1 dose level.
Grade 3 (despite standard anti-emetics)	Mandatory: Omit dose until resolved to ≤ Grade 1, then ↓ 1 dose level
Grade 4 (despite standard anti-emetics)	Mandatory: Omit dose until resolved to ≤ Grade 1, then ↓ 1 dose level
METABOLIC	
Any Grade hypophosphatemia	Recommendation: Treatment with phosphate supplements as clinically indicated and maintain dose level
Persistent hyperglycemia (glucose > 250 mg/dL, despite minimization of dose of steroids and optimal anti-hyperglycemic therapy)	Recommendation: Omit dose until hyperglycemia is adequately controlled, then resume ceritinib at ↓ 1 dose level If adequate hyperglycemic control cannot be achieved with optimal medical management, permanently discontinue patient from ceritinib.
GENERAL DISORDERS	
Fatigue (asthenia)	
Grade 1 or 2	Recommendation: Maintain dose level
Grade 3	Recommendation: If grade 3 fatigue resolves to Grade 2 in ≤ 7 days, maintain dose level If grade 3 fatigue lasts > 7 days, omit dose until resolved to ≤ Grade 2 and then ↓ dose level

Worst toxicity (CTCAE 4.03 Grade)*	Dose Modifications for ceritinib
PULMONARY	

Notes:
 
 • Recommendation: Withhold ceritinib for acute onset of new or progressive unexplained pulmonary symptoms, such as dyspnea, cough and fever and during diagnostic workup for pneumonitis/ILD. • During evaluation of potential grade 2, 3, and 4 pneumonitis, if an infectious etiology is confirmed (i.e., pneumonia) and pneumonitis is excluded, ceritinib dosing may resume at current dose level after the pneumonia resolves. 	
PNEUMONITIS	
Any Grade treatment-related ILD/pneumonitis	Mandatory: Permanently discontinue patient from ceritinib
CARDIAC	
Electrocardiogram QT corrected (QTc) interval prolonged*****	
Grade 1 (QTc 450-480 ms) Grade 2 (QTc 481-500 ms)	Recommendation: Maintain dose level
Grade 3 (QTc ≥ 501 ms on at least two separate ECGs)	
Mandatory: Omit dose until QTc is < 481ms, then ↓ 1 dose level
 
- Assess the quality of the ECG recording and the QT value and repeat if needed
 
Repeat ECG in 24 hours, or less, as clinically indicated; continue monitoring as clinically indicated until QTc < 481 ms
 
In addition:
 
 -Determine the serum electrolyte levels (in particular hypokalemia, hypomagnesemia). If abnormal, correct abnormalities before resuming study drug treatment - Review concomitant medication use for drugs with the potential to increase the risk of drug exposure related to QT prolongation - Consider collecting [REDACTED] sample and record time and date of last study drug intake 
After resumption of dosing:
 
 -Repeat ECGs 7 days after dose resumption for all patients who had therapy interrupted due to QTc ≥ 501 ms.
Grade 4 (QTc ≥ 501 or > 60 ms change from baseline and Torsades de pointes or polymorphic ventricular tachycardia or signs/symptoms of serious arrhythmia)	Mandatory: Permanently discontinue patient from ceritinib

Worst toxicity (CTCAE 4.03 Grade)*	Dose Modifications for ceritinib
Bradycardia	
Grade 1 or 2	Recommendation: Omit dose until recovery to asymptomatic bradycardia (for patients with grade 2 bradycardia) and to a heart rate \geq 50 bpm or to the baseline heart rate. Evaluate concomitant medications known to cause bradycardia, and adjust the dose of ceritinib. Exception: patients who entered the study with grade 1 bradycardia need only omit dose if bradycardia worsens to grade 2
Grade 3 Grade 4 (in patients taking a concomitant medication also known to cause bradycardia or a medication known to cause hypotension)	Mandatory: Omit dose until recovery to asymptomatic bradycardia or to a heart rate \geq 50 bpm or baseline heart rate If the concomitant medication can be adjusted or discontinued, resume ceritinib at \downarrow 1 dose level with frequent monitoring
Grade 4 (in patients who are not taking a concomitant medication also known to cause bradycardia or known to cause hypotension)	Mandatory: Permanently discontinue ceritinib.

* Common Terminology Criteria for Adverse Events (CTCAE) version 4.03. All dose modifications should be based on the worst preceding toxicity.
 
** If Grade 3 or 4 hyperbilirubinemia is due to the indirect (non-conjugated) component only, and hemolysis as the etiology has been ruled out as per institutional guidelines (e.g., review of peripheral blood smear and haptoglobin determination), then \downarrow 1 dose level and continue treatment at the discretion of the Investigator.
 
***LFTs include albumin, ALT, AST, total bilirubin, alkaline phosphatase and GGT
 
**** Dose modifications apply to patients who experience diarrhea despite appropriate antidiarrheal medication. This medication should be started at the first sign of abdominal cramping, loose stools or overt diarrhea (see Section 6.3.4.7)
 
***** Dose modifications apply to patients who experience nausea and/or vomiting despite appropriate antiemetic medication. This medication should be started at the first sign of nausea and/or vomiting (see Section 6.3.4.6.)
 
***** QTcF should be used when evaluating QT prolongation.
	

